4.2 OTHER TREATMENTS, EMERGENCY PROCEDURES, RESTRICTIONS

4.2.1 Other treatments and emergency procedures

Please refer to section 5.4.5.1 for handling patients with positive report of suicidal ideation and/or behavior.

4.2.2 Restrictions

4.2.2.1 Restrictions regarding concomitant treatment

The following restrictions for comedications are defined for this trial:

- Strong inhibitors of CYP3A4
- Strong inducers of CYP3A4 (please refer to the ISF)

A list of restricted concomitant medications and drugs with potential pharmacokinetic interactions with the trial compound BI 1358894 can be found in the ISF. The list is not

Page 58 of 148

Proprietary confidential information © 2023 Boehringer Ingelheim International GmbH or one or more of its affiliated companies

comprehensive. For example, drugs that are solely indicated for diseases that are excluded in this trial - like cancer drugs - may not be listed.

Use of ECT and Ketamine/S-Ketamine are restricted during the study, and would lead to study discontinuation (refer to section 3.3.4.1).

Patients on statins should be monitored for statin-related toxicity including signs of myopathy, weakness, muscle pain, etc. along with clinical lab results. If statins are concomitantly used during the trial, the highest dose should not be taken together with the investigational compound. If a patient in this trial is on the highest recommended statin dose, investigator should consider changing the statin dose to the next lower dose recommended for the respective statin if appropriate.

Please note:

- Investigators may use their clinical discretion to wash out (at least 3 half-lives of referenced medication) the restricted medications during the screening period. The patient must adhere to the screening visit dose of the allowed background medication for the entire duration of the trial.
- Patients who are on stable treatment with low-dose antipsychotics for treatment of insomnia or similar for at least 2 months prior to randomization should continue without change for the entire trial duration. Antipsychotic treatment for psychiatric symptoms is disallowed.
- Patients who are on stable treatment with ongoing antidepressants for at least 2 months prior to randomization should continue without change for the entire trial duration.
- Patients who are on stable treatment with ongoing benzodiazepine (including Z- drugs) or non-benzodiazepine hypnotics for at least 2 months prior to randomization should continue without change for the entire trial duration.

For patients who are not on current treatment with benzodiazepine (including Z-drugs) or non-benzodiazepine hypnotics at the time of screening, the protocol will allow concomitant use of non-benzodiazepine-, non-Z-drug hypnotics at lowest dose of the compound as noted in the Summary of Product Characteristic (or SmPC) during the trial.

- Patients who are on stable treatment with medically prescribed opioids (except fentanyl) for at least 2 months prior to randomization should continue without change for the entire trial duration. Short-term opioid therapy up to 4 weeks per time, for example with cough syrup or pain killer, is allowed (except fentanyl).
- In case of AEs, any treatment deemed necessary per the clinical judgment of investigator for the management of AEs considering patient safety is allowed.

For further guidance investigators are referred to the actual Investigator's Brochure or may contact the sponsor.

Page 59 of 148

Proprietary confidential information © 2023 Boehringer Ingelheim International GmbH or one or more of its affiliated companies

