3.3.4 Discontinuation of patients from treatment or assessments

Patients may discontinue trial treatment or withdraw consent to trial participation as a whole ("withdrawal of consent") with very different implications; please see sections 3.3.4.1 and 3.3.4.2 below.

However, if the patient agrees, they should stay in the trial: even if continued trial treatment is not possible, they should attend further trial visits to ensure their safety and to collect important trial data.

After premature study drug discontinuation, patients will be asked to further attend scheduled trial visits unless they withdraw consent to participate in the study.

It is vital to explain to patients the importance of continuing trial participation and the value of collecting data for all randomized patients.

Measures to control the withdrawal rate include careful patient selection, appropriate explanation of the trial requirements and procedures prior to trial enrolment, as well as the explanation of the options for early discontinuation and explanation of the consequences in case of withdrawals.

Page 49 of 148

Proprietary confidential information © 2023 Boehringer Ingelheim International GmbH or one or more of its affiliated companies

The decision to discontinue trial treatment or withdraw consent to trial participation and the reason must be documented in the patient files and CRF. If applicable, consider the requirements for Adverse Event collection reporting (please see section 5.4.6.2).

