Withdrawal from the trial of an individual patient may be considered also in case of administrative reasons, such as but not limited to multiple important protocol violations and persistent non-compliance. No patient should be withdrawn from the trial before discussion with the sponsor.

An individual patient will discontinue trial treatment if:

- The patient wants to discontinue trial treatment. The patient will be asked to explain the reasons but has the right to refuse to answer.
- The patient has repeatedly shown to be non-compliant with important trial procedures and, in the opinion of both, the investigator and sponsor representative, the safety of the

Page 50 of 148

Proprietary confidential information © 2023 Boehringer Ingelheim International GmbH or one or more of its affiliated companies

patient cannot be guaranteed as he/she is not willing or able to adhere to the trial requirements in the future.

- The patient needs to take concomitant medication that interferes with the investigational medicinal product or other trial treatment; refer to the ISF.
- The patient undergoes an ECT.
- Patient receives Ketamine /S-Ketamine treatment during the course of the trial.
- The patient can no longer receive trial treatment for serious medical reasons (such as surgery, adverse events, other diseases, or pregnancy), per investigator's clinical judgement. In case of a temporary reason, trial treatment should be restarted if medically justified.
- Pregnancy occurs during the trial. (Once a patient has been enrolled in the clinical trial and has taken trial medication, the investigator must report any drug exposure during pregnancy which occurred in a female trial patient to the Sponsor immediately (within 24 hours) by means of Part A of the Pregnancy Monitoring Form to the Sponsor's unique entry point).
- The patient must discontinue treatment with trial medication if the patient develops suicidal ideation of type 4 or 5 in the C-SSRS (i.e., active suicidal thought with intent but without specific plan, active suicidal thought with plan and intent) or suicidal behaviour (i.e. actual attempt, interrupted attempt, aborted attempt or preparatory acts or behavior).

In addition to these criteria, the physician may discontinue treatment at any time based on his or her clinical judgment. For all patients the reason for withdrawal from trial treatment (e.g. AEs) must be recorded in the CRF. These data will be included in the trial database and reported.

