If new efficacy/safety information becomes available, Boehringer Ingelheim will review the benefit-risk-assessment and, if needed, pause or discontinue the trial treatment for all patients or take any other appropriate action to ensure the safety of the trial patients.

Even if the trial treatment is discontinued, the patients remain in the trial and, given their agreement, will undergo the procedures for early treatment discontinuation and follow-up as outlined in the Flow Chart 1, Flow Chart 2 and section 6.2.3.

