7.2.2 Handling of Intercurrent Events

In the analyses of the primary endpoint, the following intercurrent events (ICEs) are of interest:

- 1. Change in background CNS active medication (e.g., non-SSRI antidepressant, anxiolytics)
- 2. Change in pharmacological therapy (SSRI)
- 3. Change in drug test result from negative to positive (Cannabis, Benzodiazepine, Barbiturates, Opiates, Cocaine, Amphetamines, Methadone, PCP)
- 4. Change in non-pharmacological therapy trauma-focused psychotherapy

Proprietary confidential information © 2023 Boehringer Ingelheim International GmbH or one or more of its affiliated companies

- 5. Change in non-pharmacological therapy all other cognitive/behavioral therapy (CBT) (e.g., any other kind of psychotherapy, nicotine withdrawal therapy, diet, etc.)
- 6. Withdrawal of study medication due to investigator assessed drug-related adverse events (e.g., headache)
- 7. Withdrawal of study medication due to perceived lack of efficacy or disease worsening
- 8. Withdrawal of study medication due to other adverse events
- 9. Withdrawal of study medication due to any other reasons

Table 7.2.2:1 Handling rules for Intercurrent events

	ICE	Primary Estimand	Supplementary Estimand
Handling rules for ICEs	1-4	Treatment policy	Treatment policy
	5	Treatment policy	Treatment policy
	6-7	Hypothetical	Treatment policy
	8-9	Hypothetical	Hypothetical

The primary estimand estimates the treatment effect when changes to background CNS active medication, pharmacological SSRI therapies and non-pharmacological therapies (ICEs 1-5) are considered to be part of the treatment effect, but changes to randomized treatment (ICEs 6-9) are not considered to be part of the treatment effect of interest. ICEs are therefore handled by a hybrid estimand that combines the treatment policy and hypothetical approaches, where ICEs 1-5 are handled using the treatment policy approach, and measurements taken after the occurrences of these ICEs are included in the primary analysis; ICEs 6-9 are handled using the hypothetical approach, and measurements after their occurrences are therefore censored in the primary analysis.

Page 96 of 148

Proprietary confidential information © 2023 Boehringer Ingelheim International GmbH or one or more of its affiliated companies

Regardless of the occurrence of ICEs, every attempt will be made to follow all patients until the end of the planned study period.

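### Section 4.2.2.1 says ECT or ketamine ends the study for a patient, but the section it cites ends only trial treatment, so Week 8 data could be lost to a literal reading

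*Protocol*

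**What the plan says.** The restrictions on concomitant treatment (Protocol 4.2.2.1) contain the sentence "Use of ECT and Ketamine/S-Ketamine are restricted during the study, and would lead to study discontinuation", followed by a cross-reference to 3.3.4.1.

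Section 3.3.4.1 concerns stopping trial treatment. Its list opens with "An individual patient will discontinue trial treatment if" and includes "The patient undergoes an ECT" and "Patient receives Ketamine /S-Ketamine treatment during the course of the trial". It ends by setting out the patient's status afterwards: "Even if the trial treatment is discontinued, the patients remain in the trial and, given their agreement", they go through the early-discontinuation and follow-up procedures.

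Two other sections describe what happens after the drug is stopped:
- Section 3.3.4: "After premature study drug discontinuation, patients will be asked to further attend scheduled trial visits unless they withdraw consent".
- Section 7.2.2: "Regardless of the occurrence of ICEs, every attempt will be made to follow all patients until the end of the planned study period".

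**The concern.** The protocol treats stopping the drug and leaving the trial as separate events, and 3.3.4 itself warns that their consequences differ. A patient leaves the trial by withdrawing consent (3.3.4.2), or by administrative withdrawal after discussion with the sponsor (3.3.4.1). The ECT/ketamine sentence uses the language of leaving the study and then points to a section about stopping the drug.

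A site would naturally consult 4.2.2.1 when a patient receives one of these treatments. If it takes the sentence at its word, it may cancel the remaining scheduled visits. The main loss would be the CAPS-5 at Visit 10, which is the Week 8 value. That score is used wherever the analysis follows a treatment-policy strategy after a drug stop, as the supplementary estimand does for some stops.

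**Working it through.** The point rests on comparing text, and no figure in the plan bears on it.

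**1. The trigger and its consequence**

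| Place | Trigger | Stated consequence |
|---|---|---|
| Protocol 4.2.2.1 | ECT, ketamine/S-ketamine | study discontinuation, citing 3.3.4.1 |
| Protocol 3.3.4.1, list | ECT, ketamine/S-ketamine | trial treatment stops |
| Protocol 3.3.4.1, opening and close | any stop of trial treatment | early end-of-treatment visit, remaining visits including Visit 10, and end-of-study visit, if the patient agrees |
| Protocol 3.3.4 | any premature drug stop | scheduled visits continue unless consent is withdrawn |
| Protocol 7.2.2 | any intercurrent event | every attempt to follow to the end of the planned period |

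All the passages are compatible with the drug being stopped. They differ on whether the patient stays in the visit schedule.

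**2. What a literal reading of 4.2.2.1 would lose**

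- Flow Chart 2 schedules CAPS-5 after baseline at Visit 6, Visit 10 and the early end-of-treatment visit. It does not schedule CAPS-5 at the follow-up visit (Visit 11), so attending follow-up would not recover a Week 8 score.
- SAP Table 6.7:1 assigns the early end-of-treatment assessment to a visit by study day, and the Visit 10 window opens on Day 53. A patient whose early end-of-treatment visit falls on Day 53 or later could still have a Week 8 value. The possible loss concerns earlier stops.

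**3. Which analysis would feel it**

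- Primary estimand: intercurrent events 6 to 9, the drug stops, are handled hypothetically. SAP 6.3 keeps data only to the last dose plus 7 days, so a Visit 10 score beyond that limit is censored whichever sentence the site follows. The early end-of-treatment visit, due within 7 days of the last dose, is required by Protocol 6.2.2 for any permanent stop before Week 8.
- Supplementary estimand (Protocol Table 7.2.2:1, SAP Table 6.3:1): events 6 (drug-related adverse events) and 7 (lack of efficacy or worsening) follow treatment policy, so the Week 8 score is used. Events 8 and 9 are hypothetical, so it is not.

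The exposure is therefore limited to stops for ECT or ketamine that are classed as event 6 or 7.

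**4. Safety follow-up under a literal reading**

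- Section 3.1 requires the 4-week follow-up and end-of-study visit even after a patient discontinues the trial early.
- Section 6.2.3 requires the follow-up visit for every patient who took at least one dose.
- C-SSRS is scheduled at the early end-of-treatment and follow-up visits, in the since-last-visit version.
- Adverse events are collected until the end-of-study visit (5.4.6.2.1).
- The treatment-emergent window is 28 days after the last dose (7.2.6), and the follow-up visit falls 28 to 30 days after the drug stop.

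The window therefore remains largely covered. What could disappear are the intermediate clinic and phone contacts.

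**5. Number of patients**

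The documents give no rate of ECT or ketamine use, so no count follows from them.

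**The case against.** The strongest reply is that one loose word has been made to carry too much. The sentence sends the reader to a section whose title and content concern stopping the drug. That section says patients remain in the trial, and it requires discussion with the sponsor before anyone is withdrawn. Sections 3.1, 3.3.4, 6.2.3 and 7.2.2 all provide for continued follow-up. This stands as a limit on likelihood: a premature close-out is possible, but it would run against several other passages. It does not remove the conflict, because the sentence and its own reference still name different events. Sections 3.1 and 6.2.3 protect the follow-up visit, but not Visit 10.

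A reader might infer more than the documents support:

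- **That adverse-event and C-SSRS collection would stop inside the 28-day window.** Sections 3.1 and 6.2.3 call for follow-up even after early discontinuation of the trial.
- **That the patients who worsen most would be lost, making the missing data informative.** Section 3.3.4.1 is triggered by any ECT or ketamine use and states no indication. The documents do not say who would receive either treatment, or whether use would differ by arm.
- **That a shift in the supplementary estimate can be quantified.** Both the frequency and the Week 8 scores of these patients would have to be assumed, and nothing in the documents supports a value.
- **That the SAP lacks a rule for classifying these stops.** Intercurrent events 6 to 9 already classify every withdrawal of study medication by reason, with event 9 as the remainder, and the reason is recorded in the CRF.

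**Conclusion.** The inconsistency is real and sits in operative text. Its severity is minor. The consequence is conditional: some patients' Week 8 CAPS-5 scores could be missing from the supplementary analysis if a site acts on 4.2.2.1 alone and the stop is classed as event 6 or 7. The primary result does not change, provided the early end-of-treatment visit is held as 6.2.2 requires. Safety follow-up is largely protected, provided sites apply 3.1 and 6.2.3. The number of patients affected is unknown and cannot be estimated from the protocol or SAP.

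**What to change.** Reconcile the ECT/ketamine sentence in Protocol 4.2.2.1 with 3.3.4.1, 3.3.4 and 7.2.2. All four places should name the same event and state consistently whether scheduled visits and data collection (Visit 10, C-SSRS and adverse events) continue afterwards. Which rule is intended is for the sponsor to state; the point here is only that the passages must agree.

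The cost is one sentence in the protocol, which can go into the next amendment. It adds no visits or assessments and needs no change to the SAP.

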- Any suicidal ideation of type 4 or 5 in the Columbia Suicide Severity Rating Scale (C-SSRS) in the past 3 months prior to screening or at screening or baseline visit (i.e. active suicidal thought with method and intent but without specific plan, or active suicidal thought with method, intent and plan).
- Treatment with benzodiazepines is allowed if stable in dose and frequency of use for at least 2 months prior to randomization visit. Note: PRN- use is not permitted.
- Antipsychotics, antidepressants and other psychiatric medication are allowed if stable in dose and frequency of use for at least 2 months prior to randomization visit
- Any use of restricted medications within 7 days prior to randomization visit
- Patients who must or wish to continue the intake of restricted medications or any drug considered likely to interfere with the safe conduct of the trial.
- Use of alternative medicine (e.g. Chinese traditional medicine, herbal medication, St. John's wort, etc.) during the entire course of the trial.
- History of seizure disorders, stroke, brain tumor or any other major neurological illness that can impact participation in the trial.

c34993667-05 Clinical Trial Protocol Page 5 of 148

Proprietary confidential information © 2023 Boehringer Ingelheim International GmbH or one or more of its affiliated companies

	• Resting QTcF ≥450 msec (male) or ≥460 msec (female) at screening.
	Patients who are currently involved in any ongoing legal
	processes related to the index traumatic event (e.g. lawsuit or
	criminal prosecution).
	• In-patients are generally excluded, however in-patients who are
	admittedon a voluntary basis in an open-ward (i.e. "residential
	ward") and are non-suicidal are allowed.
Test product(s)	BI 1358894
dose	125 mg; once daily
mode of	Per os
administration	
Comparator product(s)	Placebo
dose	NA for placebo
mode of	Per os
administration Duration of treatment	8 weeks
Statistical methods	
Statistical methods	Restricted maximum likelihood (REML) based approach using a
	mixed effects model with repeated measures (MMRM) will be
	utilized as the main estimator of the primary estimand on the
	primary endpoint. Intercurrent events will be handled as specified in
	Section 7. The MMRM model will include the fixed categorical
	effects of treatment at each visit, fixed categorical effect of the
	stratification factor of presence of significant childhood trauma (yes
	vs. no) according to investigator's judgement, assessed by CTQ at

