- 10. Any suicidal behavior in the past 12 months prior to screening (per investigator judgement including an actual attempt, interrupted attempt, aborted attempt, or preparatory acts or behavior) and during the screening period.
- 11. Any suicidal ideation of type 4 or 5 in the Columbia Suicide Severity Rating Scale (C-SSRS) in the past 3 months prior to screening or at screening or baseline visit (i.e. active suicidal thought with method and intent but without specific plan, or active suicidal thought with method, intent and plan).
- 12. Treatment with benzodiazepines is allowed if stable in dose and frequency of use for at least 2 months prior to randomization visit (please refer to section 4.2.2). Note: PRN- use is not permitted.
- 13. Antipsychotics, antidepressants and other psychiatric medication are allowed if stable in dose and frequency of use for at least 2 months prior to randomization visit (please refer to section 4.2.2)
- 14. Any use of restricted medications within 7 days prior to randomization visit (refer to section 4.2.2).
- 15. Patients who must or wish to continue the intake of restricted medications or any drug considered likely to interfere with the safe conduct of the trial.
- 16. Use of alternative medicine (e.g. Chinese traditional medicine, herbal medication, St. John's wort, etc.) during the entire course of the trial.
- 17. History of seizure disorders, stroke, brain tumor or any other major neurological illness that can impact participation in the trial.
- 18. Any documented active or suspected malignancy or history of malignancy within 5 years prior to screening, except appropriately treated basal cell carcinoma of the skin or in situ carcinoma of uterine cervix.
- 19. Positive result for ongoing Hepatitis B or C infection.

Page 48 of 148

Proprietary confidential information © 2023 Boehringer Ingelheim International GmbH or one or more of its affiliated companies

- 20. Known hypersensitivity to any of the excipients of BI 1358894 or the matching placebos.
- 21. Use of any investigational procedure within 30 days prior to randomization. In case of exposure to an investigational medicinal product, investigator must ensure that it is adequately washed out prior to randomization (at least 5 half-lives of the investigational medicinal product).
- 22. Resting QTcF \geq 450 msec (male) or \geq 460 msec (female) at screening.
- 23. Women who are pregnant, nursing, or who plan to become pregnant while in the trial.

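### The synopsis and exclusion criterion 13 permit stable antipsychotics whatever the dose or indication, while section 4.2.2.1 disallows them for psychiatric symptoms; the texts must be reconciled to one rule

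*Protocol*

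**What the plan says.** The synopsis, under the main exclusion criteria, reads: "Antipsychotics, antidepressants and other psychiatric medication are allowed if stable in dose and frequency of use for at least 2 months". Exclusion criterion 13 in Protocol section 3.3.3 uses the same wording and adds a bare pointer to section 4.2.2. In both places stability is the only stated condition.

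Protocol section 4.2.2.1 is narrower. Its permission covers "Patients who are on stable treatment with low-dose antipsychotics for treatment of insomnia or similar for at least 2 months prior to randomization", who are to continue unchanged. The next sentence is: "Antipsychotic treatment for psychiatric symptoms is disallowed". It makes no exception for stable use.

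Two neighbouring criteria in section 3.3.3 may also bear on the matter. Criterion 14 excludes recent use of restricted medications and refers to section 4.2.2. Criterion 15 excludes "Patients who must or wish to continue the intake of restricted medications".

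**The concern.** One current text permits what another forbids, and both govern who may enter the trial and on what background treatment. About 70 centres in 10 countries are planned (Protocol section 3.3). Each must hold documented evidence that a patient meets no exclusion criterion (Protocol section 8.3.1). A site that works from criterion 13 can enrol a patient whom a site working from section 4.2.2.1 would turn away.

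The choice of text also affects what happens next:

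- **Washout.** Section 4.2.2.1 holds allowed background medication at its screening dose but lets investigators wash out restricted medication during screening. Which instruction covers this patient's antipsychotic depends on the unresolved question.
- **Deviation status.** Protocol section 3.3 requires immediate contact with the sponsor and an individual decision on continuing when a patient was randomised in error. The text does not settle whether this patient was.

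**Working it through.** No arithmetic applies, and the plan states no figure on this point. The check is a comparison of texts.

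**Step 1: apply each rule to three kinds of patient, all stable for at least 2 months.**

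| Antipsychotic use | Synopsis and criterion 13 | Section 4.2.2.1 | Result |
|---|---|---|---|
| Low dose, for insomnia | Permitted | Permitted | No conflict |
| Any dose, for psychiatric symptoms | Permitted | Disallowed | Direct conflict |
| Above low dose, for insomnia | Permitted | Outside the permission, not expressly disallowed | Unclear |

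The direct conflict is confined to the second row.

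**Step 2: does the pointer in criterion 13 resolve it?** The pointer sends the reader to the section that holds the limit, so the criterion can be read as subject to it. But the criterion does not say that its permission is conditional, and its wording still permits what the section forbids. The synopsis has no pointer.

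**Step 3: do criteria 14 and 15 resolve it?** They would remove the patient if a disallowed antipsychotic is a restricted medication. Section 4.2.2.1 opens its list with "The following restrictions for comedications are defined for this trial" and then names strong CYP3A4 inhibitors and strong CYP3A4 inducers. It later calls ECT and ketamine restricted as well. For antipsychotics it uses a different word. Other restricted drugs are in an investigator site file list that is not part of the documents. This route is arguable but cannot be confirmed.

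**Step 4: does any other text resolve it?** Protocol section 1.4.3 lets patients continue stable psychiatric medication, but its explanatory bracket names only non-benzodiazepine anxiolytics and does not mention antipsychotics. The amendment descriptions in Protocol section 11 contain no entry on antipsychotics.

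**Step 5: does the analysis plan pick it up?** Intercurrent event 1 (Protocol section 7.2.2, SAP section 6.3) is a change in background CNS-active medication. An antipsychotic taken unchanged from baseline is not such a change. What remains is deviation handling under SAP section 6.2, which needs a settled protocol rule to judge against.

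**The case against.** The strongest reply is that the protocol can be read as coherent. Criterion 13 stands in an exclusion list, so it may work only as an exclusion of unstable treatment. Passing it does not make anyone eligible, because every other criterion must also be cleared. Its pointer leads to the section with the limit, and criteria 14 and 15 can exclude the patient. The synopsis is a summary that also drops the same pointer elsewhere, so its silence is not a separate rule. Sites may ask the sponsor for guidance.

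Much of this stands. A reader might infer that such a patient is plainly eligible, or that the permission is unconditional. The documents support neither, given the pointer and the possible reach of criteria 14 and 15. But the coherent reading needs a disallowed antipsychotic to count as restricted, which the visible text does not say. It also needs the reader to treat an express permission as overridden by a cross-reference that does not announce this.

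The second reply concerns the analysis, and it also stands:

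- Important deviations are assessed at central meetings, and exclusions are settled at the final report planning meeting before database lock (SAP section 6.2).
- The primary analysis uses the FAS (Protocol section 7.2.3, SAP section 7.4.1).
- A per-protocol analysis is an optional sensitivity analysis, considered only if more than 10% of the FAS would be excluded (SAP section 6.4).
- Eligibility is decided before a blinded 1:1 randomisation, so uneven reading of the rule gives no reason to expect a systematic difference between arms.

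**Conclusion.** The point holds as an internal contradiction in current protocol text, limited to patients on a stable antipsychotic for psychiatric symptoms. Stable low-dose use for insomnia is not in conflict. Use for insomnia above a low dose is left unclear. Sites following the text could reach opposite decisions on enrolment, washout and deviation status. It is not established that they will, because the site file list and any sponsor guidance cannot be seen.

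The size cannot be stated. The documents give no share of patients on antipsychotics, so any count out of the planned 286 would rest on an assumption with no anchor in them. The contradiction does not depend on the number. Criterion 1 already excludes psychotic and bipolar disorders, which narrows the group.

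A reader might also infer that the primary result would be biased or the per-protocol set distorted. The documents do not support that: randomisation protects the FAS comparison, and exclusions from the per-protocol set are decided centrally. What is at stake is consistent enrolment and a clear standard for calling a deviation. This should be corrected, but it does not threaten the primary analysis.

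**What to change.** The sponsor must reconcile the synopsis, criterion 13 (together with criteria 14 and 15) and section 4.2.2.1 to one rule on which stable antipsychotic use is permitted. No view is taken here on what that rule should be. Three wording changes follow:

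1. State the rule in criterion 13 itself, so that it does not rest on a cross-reference, and repeat it in the synopsis.
2. Say whether a disallowed antipsychotic is a restricted medication for criteria 14 and 15, and align the site file list.
3. Use the same rule in the important-deviation specifications under SAP section 6.2, so that patients already randomised are classified alike.

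The cost is wording in a protocol amendment or clarification letter and a matching line in the deviation specifications. The sample size, the estimand and the primary model are unchanged.
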